9.2. Handling of incomplete dates

Missing dates should be treated as “undescribed”. Dates including unknow date, month or year, or dates that cannot be true according to the calendar should be handled as “unknown” without exception.

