9.1. Handling of missing data

Missing data should not be complemented in the analysis.

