10.1. Overall

Name of data	Derivation and calculation methods
Age	The age on the start date of treatment should be calculated. However, if the birth date is unknown, the age described in the CRF should be used. Since it is obtained up to birth month and year in the CRF, the birth date should be the 1st of the month.
Number of survey institutions	It should be tabulated by institution code.
Number of patients surveyed	It should be tabulated by case (number).
Calculation of period	Period = the relevant date - the initial date +1
Definition of unit period	One week should be converted into seven days.
Date of initial Humira treatment	Of the start dates of treatment in Humira treatment status, the earliest date should be the date of initial Humira treatment.
Date of final Humira treatment	
Of the completion dates of treatment in Humira treatment status, the latest date should be the date of final Humira treatment.
 
However, the following measures should be taken according to the final record of each patient.
 
 • For patients whose the start date of treatment exceeds the planned completion date of each CRF and the completion date of treatment is described as “continuing,” the start date of treatment should be complemented to the complete date of treatment of the record. • For patients whose the start date of treatment is prior to the planned completion date of each CRF and the completion date of treatment is described as “continuing,” the completion date of treatment should be complemented to the complete date of treatment of each CRF. • If the start date of treatment with a biological product and the final record of the completion date of Humira treatment are the same date in the third CRF, the completion date of Humira treatment should be -1 day and the overlap of the treatment period should be deleted. 
*Planned completion date of each CRF First CRF: start date of Humira treatment + 167 days Second CRF: start date of Humira treatment + 363 days Third CRF: start date of Humira treatment + 727 days

Period to treatment completion (day)	It should be between the date of initial Humira treatment and the date of final Humira treatment.

Name of data	Derivation and calculation methods

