Presence of complication: others	Patients with the complication items applicable to the details of blood disorders [diabetes mellitus, gastrointestinal disorder, osteoporosis, malignant tumour, demyelinating disorders, collagen disorders (other than rheumatoid arthritis), others] should be handles as “present,” when there is no description in the presence of complications, it should be handled as “undescribed,” respectively, and others should be handled as “absent.”
Presence of a past history	When any of the details of the past history is evaluated as present, it should be handled as “present,” when it is described as no complication, it should be handled as “absent,” and when there is no description both in past history and the details, it should be handled as “undescribed.”

Name of data	Derivation and calculation methods
Presence of a history of allergy	If there is nothing applicable to a history of allergy, it should be handled as “undescribed.” In the details, if the patient is applicable to both “drugs” and “food,” it should be handled as “both.”
RA stage/progression	If there is no description in the RA stage/progression, it should be handles as “undescribed.”
Disabilities in RA	If there is no description in the RA disability index, it should be handles as “undescribed.”
Presence of concomitant drugs (At start date of Humira treatment)	If there is any drug administration on the date of initial Humira treatment, it should be handled as “present,” and others should be handled as “absent.”
Presence of concomitant drugs (During treatment with Humira)	If there is any drug administration during treatment with Humira, it should be handled as “present,” and others should be handled as “absent.” Administration during treatment with Humira refers to all administration cases not applicable to the followings. 
 • The completion date of treatment with a concomitant drug is prior to the date of initial Humira treatment • The start date of treatment with a concomitant drug is after the date of final Humira treatment
Concomitant drug: MTX (mg/week)	The dose of MTX during the period including the date of initial Humira treatment should be sorted into the following three categories: “ ≥ 12.0 mg/week and < 14.0 mg/week,” “ ≥ 14.0 mg/week and < 16.0 mg/week,” and “ ≥ 16.0 mg/week.”

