Evaluation time for evaluation of treatment continuing group and treatment discontinued group in the third CRF should also be allocated separately for the data entered at the evaluation time of mTSS, bone erosion score and joint space narrowing score. For patients whom the final Humira treatment is later than week 52 +4 weeks, the data on the latest date in the third CRF should be used as the data on the final evaluation date of X-ray. However, if there is the date of survey discontinuation, the data up to the date should be used.

This date is called [final evaluation date of X-ray] in the following.

At final evaluation (third CRF)	
When the date of survey discontinuation is not entered: The final data of the patient among the data included in the period between the date of initial Humira treatment +504 days and the final evaluation date of X-ray (should be later than day 505) should be adopted.
 
When the date of survey discontinuation is entered: The final data of the patient among the data included in the period between the date of initial Humira treatment +504 days and the final evaluation date of X-ray (should be later than day 505) should be adopted.
 
In the treatment discontinued group, the data of which the date of treatment discontinuation and the final evaluation date of X-ray are ≥ 24 weeks apart should be adopted.

---------------------------------	--

When tabulating AEs by time of onset, the tabulation subjects should be decided based on the followings. If there is more than one event of the same PT in the same patient, its tabulation should be focusing on the initial occurrence.

However, when extraction conditions including seriousness and causal relationship are added to the AEs, its tabulation should be focusing on the initial occurrence after narrowing them down with the extraction conditions. In addition, the data on AEs outside the follow-up period among the data included in the following acceptable range should also be excluded from tabulation.

Timing and period category	Handling of data
Treatment start to week 24	Data included in the period between the date of initial Humira treatment and the date of initial Humira treatment +167 days should be adopted.
Week 24 to week 52	Data included in the period between the date of initial Humira treatment +168 days and the date of initial Humira treatment +363 days should be adopted.

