Analysis object: Patients included in the safety analysis set

Purpose of analysis: To indicate the number of patients analyzed, number of patients who developed all events, number and percentage of ADRs, number and percentage of SOC and PT by seriousness regarding ADRs. The same PT of the same patient should be summarized collectively, and in that sense, the most serious event should be tabulated.

Note: The information on novelty should not be granted.

The next forms should be prepared in the same manner.

“Table 5.1.1 Frequency of AEs by seriousness”

Analysis object: Patients included in the safety analysis set

“Table 5.1.2 Frequency of ADRs by seriousness (excluded patients)”

Analysis object: Patients excluded from the safety analysis set

Note: Among the patients with fixed CRFs, the patients excluded from the safety analysis set should be tabulated.

“Table 5.1.3 Frequency of ADRs by seriousness (Hospital of the University of Occupational and Environmental Health, Japan)”

Analysis object: Patients included in the safety analysis set

Note: patients treated at the Hospital of the University of Occupational and Environmental Health, Japan should be tabulated.

“Table 5.1.4 Frequency of ADRs by seriousness (other than Hospital of the University of Occupational and Environmental Health, Japan)”

Analysis object: Patients included in the safety analysis set

Note: Patients excluded from those treated at the Hospital of the University of Occupational and Environmental Health, Japan should be tabulated.

“Table 5.2.1 Frequency of ADRs by time of onset”

Analysis object: Patients included in the safety analysis set

Purpose of analysis: To indicate the number of patients analyzed, number of patients who developed all ADRs, number and percentage of ADRs, number and percentage of SOC and PT by time of onset regarding ADRs.

Note: The information on novelty should not be granted.

Categories for time of onset of ADRs: “start of treatment to week 24,” “week 24 to week 52,” “week 52 to week 108,” and “after completion of treatment.”

“Table 5.2.2 Frequency of serious ADRs by time of onset”

Analysis object: Patients included in the safety analysis set

Purpose of analysis: To indicate the number of patients analyzed, number of patients who developed all events, number and percentage of ADRs, number and percentage of SOC and PT by time of onset regarding serious ADRs.

Note: The information on novelty should not be granted.

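### SAP 9.2 discards a known month and year when the day is missing, so a month-only ADR has no place in the time-split safety tables

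*SAP*

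**What the plan says.** SAP 9.2 (Handling of incomplete dates) gives one rule for every partial or impossible date: "Dates including unknow date, month or year, or dates that cannot be true according to the calendar should be handled as “unknown” without exception". SAP 9.1 adds: "Missing data should not be complemented in the analysis".

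Several safety outputs need a date:

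- **Tables 5.2.1 and 5.2.2 (SAP 13.2)** report ADRs and serious ADRs by onset. The note headed "Categories for time of onset of ADRs" lists four: start to week 24, weeks 24 to 52, weeks 52 to 108, and after completion of treatment. SAP 12 defines the first three by day count. For the first: "Data included in the period between the date of initial Humira treatment and the date of initial Humira treatment +167 days should be adopted". The next two run from +168 to +363 and from +364 to +755 days.
- **Tables 5.3.1 and 5.3.2** split events in patients who discontinued at the date of final Humira treatment.
- **Table 5.2.4** divides serious ADRs during Humira treatment by total follow-up.

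None of these has a category for an unknown onset date.

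For baseline methotrexate (MTX), SAP 10.1 says: "The dose of MTX during the period including the date of initial Humira treatment should be sorted into the following three categories". Neither SAP 10.1 nor SAP 11 gives that item an unknown level, although SAP 11 has unknown or undescribed levels for weight, duration of illness, allergy and smoking.

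**The concern.** The rule goes further than declining to impute: it removes information that was recorded. A reaction reported for a month that lies wholly inside the first 24 weeks is plainly a first-window event, yet under 9.2 it has no onset date and no column.

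At stake is the description of when reactions occur. The time columns would no longer account for all the reactions in the overall count, and nothing in the table would show why. Table 5.2.4 matters most because it is a rate: events can be lost from the top with no matching loss from the bottom, so any error of this kind lowers the serious-ADR rate.

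For MTX, the SAP does not say what happens when the record that should cover the first Humira date has a partial start date. The programmer has to decide.

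**Working it through.** The plan states no figure for this point, so there is none to reproduce. The check has three steps.

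**1. What follows from the text for a month-only ADR**

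| Output | Date needed? | Result under 9.2 |
|---|---|---|
| 5.1, 5.4 | No split by date | Counted |
| 5.2.1, all-ADR count | No onset category needed | Can be counted |
| 5.2.1, 5.2.2, four onset categories | Yes | No category |
| 5.3.1, overall and continuing groups | No during/after split needed | Can be counted |
| 5.3.1, 5.3.2, discontinued patients, during/after | Yes | Neither column |
| 5.2.4, serious ADRs during treatment | Yes, in discontinued patients | Cannot be shown to qualify |

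Table 5.2.1 does call for the "number of patients who developed all ADRs, number and percentage of ADRs, number and percentage of SOC and PT by time of onset", so the total survives but its breakdown by time does not. SAP 10.2 excludes events dated before the start of treatment or beyond the follow-up limit. It does not name an unknown date as a reason for exclusion.

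For Table 5.2.4, let S be the serious ADRs truly during treatment, k those whose status becomes unknown, and T the follow-up. The rate moves from S/T to (S − k)/T, a ratio of 1 − k/S. The documents give neither k nor S.

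**2. How much the month alone would settle**

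Inputs: windows of days 0-167, 168-363 and 364-755 (SAP 12), which are 168 + 196 + 392 = 756 days; first Humira dates from September 2012 to December 2014 (Protocol 7.5). Assumption, not in the documents: onset is uniform over the 756 days. A month counts as settled when all its days fall in one window.

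Worked example, first Humira date 10 March 2013:

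- Window 1 ends on 24 August 2013 (day 167), window 2 on 8 March 2014 (day 363), window 3 on 4 April 2015 (day 755).
- The months that straddle a boundary, with their days inside follow-up, are March 2013 (22), August 2013 (31), March 2014 (31) and April 2015 (4). Total: 88.
- Settled: (756 − 88)/756 = 668/756 = 88.4%.
- A reaction to Humira cannot precede the first dose, so March 2013 can be assigned to window 1: (756 − 66)/756 = 690/756 = 91.3%.

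Over every start date in the recruitment period:

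| Version | Lowest | Mean | Highest |
|---|---|---|---|
| Whole month in one window | 84% | 88% | 93% |
| Same, with days before the first dose ruled out | 88% | 90% | 95% |

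**3. During or after treatment**

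One treatment end date leaves at most one calendar month ambiguous. With a 31-day month, (756 − 31)/756 = 95.9% are settled; with a 28-day month, (756 − 28)/756 = 96.3%. The mean over the start and end dates tried was about 96%.

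**The case against.** The strongest reply is that a reaction loses its time column, not its place in the safety evaluation. That is correct. A reader might infer that month-only ADRs vanish from every onset and during/after table; step 1 shows that they do not.

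Four further points on that side:

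- **Site comparison.** A reader might infer that sites with poorer records would look safer. The planned site comparisons (Tables 1.4, 5.1.3, 5.1.4, 5.4.1 and 5.4.2) do not use onset time, and no onset table is split by site. The documents do not support the inference.
- **MTX class.** One might assume that some share of dates is partial and convert it into a number of the 350 planned patients who lose their dose class. The documents give no such share, 350 is an enrolment target, and the SAP nowhere says that such records are dropped; the MTX records it does exclude are those with a dose of 0 mg. Loss of the class is a reading of silence. Protocol 7.6.2 also collects MTX from 6 months before adalimumab, so the dose at Humira start may well be known.
- **Data cleaning.** Completeness checks and site queries (Protocol 11.0) and the matching of CRF and safety data (SAP 10.2) may resolve many partial dates. That limits the size of the problem; it does not supply a rule for the dates that remain.
- **Birth date.** SAP 10.1 says: "Since it is obtained up to birth month and year in the CRF, the birth date should be the 1st of the month". This sits badly with the words without exception in 9.2, but it is a derivation for a field collected only to the month. It shows that the SAP will work from a month; it is not a serious contradiction.

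Completing every partial date would also be wrong. If month-only MTX starts went to the 1st and stops to month-end, two records with a dose change in the same month would overlap throughout it. SAP 10.1 resolves only same-date hand-overs and overlaps at the same dose.

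**Conclusion.** The point holds in a limited form. SAP 9.2 is an explicit rule that discards usable timing, and the time-split safety tables have nowhere to put the result. The consequences are an unexplained gap between the onset columns and the overall ADR count, events in discontinued patients with no during/after status, and a possible downward error in the Table 5.2.4 rate.

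The size is unknown because the number of partial dates is unknown. What can be said, under uniform onset, is that the month would settle the window for about 84-95% of affected onsets and the during/after status for about 96%. Onset concentrated near a window boundary or a treatment end date would lower those shares.

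The primary endpoint is not involved, and the affected safety tables are descriptive. For baseline MTX dose the fault is a missing instruction, not a demonstrated loss of patients. The change is worth making because it is cheap and clearly better than the stated rule.

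**What to change.** 1. Amend SAP 9.2, and state the exception to 9.1, so that a known year and month are used whenever they place a date unambiguously before, within or after a window or treatment period. Otherwise keep the date as unknown.
2. Add an onset-date-unknown column to Tables 5.2.1, 5.2.2, 5.3.1 and 5.3.2 so that they reconcile with the overall counts.
3. For Table 5.2.4, show the rate with and without serious ADRs whose during/after status stays unknown.
4. For baseline MTX, state that a record whose known start month is before the first Humira date, and whose stop is after it, covers that date. Add an unknown class for the rest. Do not complete month-only starts to the 1st and stops to month-end.

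The cost is SAP wording and a short programming step, with a few events left in the unknown column.

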9.3. Descriptive statistics

The followings should be calculated for categorical data and quantitative data.

Type of data	Items to be calculated
Categorical data	Number of patients, percentage
Quantitative data	Number of patients, mean, standard deviation (SD), median, minimum, maximum, etc.

9.4. Number of digits shown

The number of digits expressed is as follow.

Numeric type	Number of digits expressed
Mean, SD, median, 95% confidence interval (CI)	The figures should be rounded to +2 significant digits of the data, and expressed to +1 significant digit.
Minimum, maximum	Figures should be displayed with the same number of digits as the displayed digits of the data.
Number of patients	The figures should be expressed in integer values.
Percentage, rate	The incidence of AEs (including ADRs) should be rounded to the second decimal place and expressed to two decimal places. Those other than the incidence of AEs (including ADRs) should be rounded to the first decimal place and expressed to one decimal place.
p value	The figures should be rounded off to the fourth decimal place and expressed to four decimal places. However, if the figure is smaller than 0.0001, it should be expressed as $p < 0.0001$ without exception.
Number of significant digits	1 [age, total number of Humira doses, period to completion of treatment (day), tender joint count, swollen joint count, ESR] 0.1 [duration of illness, duration of smoking, weight, MTX dose, DAS28-4ESR, DAS28-4CRP, CDAI, SDAI, VAS, HAQ, mTSS, bone erosion score, joint space narrowing score] 0.01 [CRP] 0.001 [EQ5D]

9.5. Numerical expression rule

Case	Expression rule
When figures are incalculable	Hyphen “-”

9.6. Level of significance

In principle, the significance level of statistical analysis used in this survey is two-sided 5%. $p < 0.05$ ($< 5\%$) should be considered significant.

9.7. Diagram-specific rules

- 1) Appended Form 2, Appended Form 10, Appended Form 3
 - A) Forms should be created in accordance with the latest version of “Guidance for Application for Reexamination, Japan Pharmaceutical Information Center”
 - B) Separation of the reporting period for Appended Form 2 and Appended Form 10 is as follows.
In principle, this should be the survey unit period defined in the analysis implementation schedule. However, the period should be determined upon consultation with the sponsor.

10. Data derivation and calculation methods

10.1. Overall

Name of data	Derivation and calculation methods
Age	The age on the start date of treatment should be calculated. However, if the birth date is unknown, the age described in the CRF should be used. Since it is obtained up to birth month and year in the CRF, the birth date should be the 1st of the month.
Number of survey institutions	It should be tabulated by institution code.
Number of patients surveyed	It should be tabulated by case (number).
Calculation of period	Period = the relevant date - the initial date +1
Definition of unit period	One week should be converted into seven days.
Date of initial Humira treatment	Of the start dates of treatment in Humira treatment status, the earliest date should be the date of initial Humira treatment.
Date of final Humira treatment	
Of the completion dates of treatment in Humira treatment status, the latest date should be the date of final Humira treatment.
 
However, the following measures should be taken according to the final record of each patient.
 
 • For patients whose the start date of treatment exceeds the planned completion date of each CRF and the completion date of treatment is described as “continuing,” the start date of treatment should be complemented to the complete date of treatment of the record. • For patients whose the start date of treatment is prior to the planned completion date of each CRF and the completion date of treatment is described as “continuing,” the completion date of treatment should be complemented to the complete date of treatment of each CRF. • If the start date of treatment with a biological product and the final record of the completion date of Humira treatment are the same date in the third CRF, the completion date of Humira treatment should be -1 day and the overlap of the treatment period should be deleted. 
*Planned completion date of each CRF First CRF: start date of Humira treatment + 167 days Second CRF: start date of Humira treatment + 363 days Third CRF: start date of Humira treatment + 727 days

Period to treatment completion (day)	It should be between the date of initial Humira treatment and the date of final Humira treatment.

Name of data	Derivation and calculation methods
Treatment period (day) Completion date of treatment *Per record	
It should be between the start date of Humira treatment and the completion date of treatment per treatment record.
 
When the completion date of treatment in the information on the previous treatment within the same CRF and the start date of treatment in the information on the relevant treatment are the same date, the completion date of treatment in the information on the previous treatment should be - 1 day.
 
The records with the dose of 0 mg should be excluded from the analysis.

Dosing intervals (day) *Per record	Biweekly should be 14 days, once in three weeks should be 21 days, and once in four weeks should be 28 days, respectively.
Total number of doses	The total after calculating the number of doses per record by rounding up the first decimal place should be taken for treatment period (day)/dosing intervals (day).
Patients who discontinued Humira treatment	If the final fixed CRF is the first or second CRF, the patients should be handled as the patients with a description in the “treatment discontinuation” column in the final CRF. If the final fixed CRF is the third CRF, the patient should be handled as the patients with a description of the completion date of treatment in the final record of the “Humira treatment status” column in the final CRF.
Patients who are continuing Humira treatment	If the final fixed CRF is the first or second CRF, the patients should be handled as the patients without a description in the “treatment discontinuation” column in the final CRF. If the final fixed CRF is the third CRF, the patient should be handled as the patients with a description of “continuing” in the final record of the “Humira treatment status” column in the final CRF.
Date of treatment discontinuation	In patients who discontinued Humira treatment, the completion date of Humira treatment should be the date of discontinuation.
Low body weight	Patients with body weight of < 30 kg.
Date of survey discontinuation	It should be the date of survey discontinuation described in the third CRF. It should be the start date of treatment with other biological products, or the older date among the last follow-up date.
AE follow-up period	It should be between the date of initial Humira treatment and the date of initial Humira treatment + 755 days.
Presence of complications	When any of the details of the complication is evaluated as present, it should be handled as “present,” when it is described as no complication, it should be handled as “absent,” and when there is no description both in complication and the details, it should be handled as “undescribed.”

Name of data	Derivation and calculation methods
Presence of complication: liver disorders	Patients with the complication items applicable to the details of liver disorders (hepatitis, hepatitis virus carrier, hepatic cirrhosis, hepatic steatosis, others) should be handles as “present,” when there is no description in the presence of complications, it should be handled as “undescribed,” and others should be handled as “absent.”
Presence of complication: renal disorders	Patients with the complication items applicable to the details of renal disorders (nephritis, renal failure, nephrotic syndrome, others) should be handles as “present,” when there is no description in the presence of complications, it should be handled as “undescribed,” and others should be handled as “absent.”
Presence of complication: cardiovascular disorders	Patients with the complication items applicable to the details of cardiovascular disorders (cardiac failure, angina pectoris, arrhythmia, hypertension, others) should be handles as “present,” when there is no description in the presence of complications, it should be handled as “undescribed,” and others should be handled as “absent.”
Presence of complication: blood disorders	Patients with the complication items applicable to the details of blood disorders (anaemia, aplastic anaemia, pancytopenia, others) should be handles as “present,” when there is no description in the presence of complications, it should be handled as “undescribed,” and others should be handled as “absent.”
Presence of complication: respiratory disorders	Patients with the complication items applicable to the details of respiratory disorders [interstitial pneumonia, asthma, obstructive pulmonary disease, bronchitis bacterial, nontuberculous mycobacteriosis (including colonization), others] should be handles as “present,” when there is no description in the presence of complications, it should be handled as “undescribed,” and others should be handled as “absent.”
Presence of complication: others	Patients with the complication items applicable to the details of blood disorders [diabetes mellitus, gastrointestinal disorder, osteoporosis, malignant tumour, demyelinating disorders, collagen disorders (other than rheumatoid arthritis), others] should be handles as “present,” when there is no description in the presence of complications, it should be handled as “undescribed,” respectively, and others should be handled as “absent.”
Presence of a past history	When any of the details of the past history is evaluated as present, it should be handled as “present,” when it is described as no complication, it should be handled as “absent,” and when there is no description both in past history and the details, it should be handled as “undescribed.”

Name of data	Derivation and calculation methods
Presence of a history of allergy	If there is nothing applicable to a history of allergy, it should be handled as “undescribed.” In the details, if the patient is applicable to both “drugs” and “food,” it should be handled as “both.”
RA stage/progression	If there is no description in the RA stage/progression, it should be handles as “undescribed.”
Disabilities in RA	If there is no description in the RA disability index, it should be handles as “undescribed.”
Presence of concomitant drugs (At start date of Humira treatment)	If there is any drug administration on the date of initial Humira treatment, it should be handled as “present,” and others should be handled as “absent.”
Presence of concomitant drugs (During treatment with Humira)	If there is any drug administration during treatment with Humira, it should be handled as “present,” and others should be handled as “absent.” Administration during treatment with Humira refers to all administration cases not applicable to the followings. 
 • The completion date of treatment with a concomitant drug is prior to the date of initial Humira treatment • The start date of treatment with a concomitant drug is after the date of final Humira treatment
Concomitant drug: MTX (mg/week)	The dose of MTX during the period including the date of initial Humira treatment should be sorted into the following three categories: “ ≥ 12.0 mg/week and < 14.0 mg/week,” “ ≥ 14.0 mg/week and < 16.0 mg/week,” and “ ≥ 16.0 mg/week.”
Start date of MTX treatment *Per record	When there is more than one record of the same reason for use and same dose within the same patient and the treatment period is overlapped in these records, the information in the record in the latest CRF should be adopted and the start date of MTX treatment of the record should be used. The records with the dose of 0 mg should be excluded from the analysis.
Completion date of MTX treatment *Per record	When the completion date of treatment in the information on the previous treatment and the start date of treatment in the information on the relevant treatment are the same date within the same patient, the completion date of treatment in the information on the previous treatment should be - 1 day.
Treatment continuing group	Among the patients included in the efficacy analysis set (third CRF), patients who are continuously receiving Humira at week 104.

Name of data	Derivation and calculation methods
Treatment discontinued group	Among patients included in the efficacy analysis set (third CRF), patients whom the discontinuation date of Humira treatment and the relevant date at week 104 is ≥ 24 weeks apart of the patients continuing the survey who discontinued Humira treatment later than week 52. Or the patients whom the date of final follow-up (or the lower date of the start date of treatment with other biological product other than Humira) is ≥ 24 weeks apart from the date of Humira treatment discontinuation among the patients discontinued survey who discontinued Humira treatment later than week 52.
Survey discontinued group	Among the patients included in the efficacy analysis set (third CRF), the patients with the entry of the start date of treatment with other biological products other than Humira or the final follow-up date not applicable to the conditions for the treatment discontinued group.
Other groups	Among the patients included in the efficacy analysis set (third CRF), patients who are not applicable to the treatment continuing group, treatment discontinued group or survey discontinued group.
Mode of administration	
All modes of administration during the Humira treatment period should be summarized, and indicated by five levels of category:
 
administration by a physician only, administration by a physician to self-administration, self-administration only, self-administration to administration by a physician, and administration by a physician and self-administration alternatively.
 
When tabulating, the patients should be categorized by “administration by a physician only” for patients who received Humira by administration by a physician only, “self-administration only” for patients with self-administration only, and “administration by a physician and self-administration” for patients received in both modes of administration and should be tabulated by group.

Dosage and administration	
Dosage and administration should be indicated by the following four levels of categories:
 
40 mg/biweekly, 80 mg/biweekly, 40 mg/biweekly or 80 mg/biweekly, other
 
.

